The DSMB will not meet regularly during Cohort 1 unless the Sponsor seeks an independent DSMB review based on Sponsor or Ethics Committee (EC) recommendations for managing AEs.

3.2. Cohort 2

Upon confirmation of histological response in Cohort 1 subjects, demonstrating engraftment and the potential for clinical efficacy at a higher (therapeutic) dose, enrollment in the Efficacy Cohort 2 will be initiated.

In Cohort 2, the Screening Period for each subject is expected to be approximately five (5) weeks in duration and comprised of two (2) study visits. Subjects qualifying for entry into Cohort 2 and who subsequently are implanted with VC-01 sentinel units and/or dose-finding units (VC-01-DF) may complete an additional 12 visits over a period of approximately one (1) year. It is expected that a subject who completes the planned entire duration of the trial will therefore have a total of 14 study visits spanning approximately 13 ½ months (including Screening, Treatment Period, and final Follow-up Visit). If the Sponsor has planned/scheduled an earlier explant (for non-safety reasons), this subject will also be considered as completing the study early (ET) with fewer study visits, as applicable.

Up to 40 subjects will receive subcutaneous implantation of:

- O Up to nine (9) VC-01-DF units, or;
- Up to 12 units total. Of the 12 units, no more than nine (9) will be dose-finding (VC-01-DF) and the remainder may be sentinel units. For example, if seven (7) VC-01-DF units are implanted in a subject, up to five (5) sentinels may be implanted.

The number of VC-01-DF units to be implanted in Cohort 2 subjects will be a data-driven decision and may vary between subjects. The Sponsor will review available C-peptide results from ongoing subjects to determine the optimal number of VC-01-DF units to implant in subsequent subjects. The Sponsor generally intends to implant the least number of VC-01-DF units required to provide the intended therapeutic benefit. Pre-clinical data suggest VC-01-DF units may provide enough therapeutic benefit to allow a subject to discontinue exogenous insulin. However, if VC-01 does not function as robustly in humans as observed in pre-clinical models, then the number of VC-01-DF units required may be

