Note: A subject whose final explant is expedited at the request of the Sponsor to occur prior to Week 26 (Cohort 1) or Week 52 (Cohort 2) for reasons unrelated to safety issues (e.g., the Sponsor would like to collect all explant data from the subject by Week 12) will be categorized as having completed the study. These subjects will not be classified as Early Terminations.

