13.6.1. Handling of Withdrawals

Subjects who are withdrawn prematurely from the study will have the remaining VC-01 units explanted. If a subject withdraws from the trial and also withdraws consent for disclosure of future information in writing, no further evaluations should be performed, and no additional data should be collected. The Sponsor may retain and continue to use any data collected before withdrawal of consent.

If a subject does not return for a scheduled visit, every effort should be made to contact the subject. It is recommended that three (3) attempts by telephone and at least three (3) attempts by certified letter should be made to contact the subject. All attempts to contact the subject must be documented in the subject's source record. Procedures will be put in place at each site to ensure that if a subject loses contact with the trial site, alternative measures will be utilized for the collection of information. This may include contacting family members and health care providers and, when appropriate, using subject location services. In all circumstances, every effort should be made to document the subject's outcome, if possible, and to advise the subject to return to the clinic for explantation of the sentinels.

Subjects who have not withdrawn consent, but who have been discontinued from the main study prematurely (with products explanted) will be rolled over into separate, long-term, follow-up trial. Those subjects may initiate any other therapy as needed to treat diabetes and any other concurrent medical conditions.

Withdrawal due to AE should be distinguished from withdrawal due to insufficient response and recorded on the appropriate AE CRF page. When a subject withdraws due to an SAE, the SAE must be reported in accordance with the reporting requirements defined in **Section 8.2**. The reason for discontinuation will be documented in the subject's source records.

For safety reasons, all Early Termination procedures (including explantation procedure) as described in Visit 11/ET and Visit 12 (Cohort 1) or Visit 13/ET and Visit 14 (Cohort 2) should be performed if a subject discontinues the trial.

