## Cohort 2 – Safety and Efficacy

*Up to 40 subjects may be enrolled and receive subcutaneous implantation of:* 

- *Up to nine (9) VC-01-DF units, or;*
- Up to 12 units total. Of the 12 units, no more than nine (9) will be VC-01-DF and the remainder will be sentinel units. For example, if seven (7) VC-01-DF units are implanted in a subject, up to five (5) sentinels may be implanted.

The sentinel units may be explanted at varying time points post-implant to assess graft cell viability, differentiation, vascularization, and host response. At the discretion of the Sponsor and after consultation with the Investigator, explantation of up to two (2) VC-01-DF units is allowed at any time post-implant without needing to withdraw the subject from the study.

Total duration of treatment may be up to one (1) year for each Cohort 2 subject, with the last unit explanted at Month 12/Week 52 or earlier if requested by the Sponsor. Cohort 2 subjects will complete a total of up to 14 study visits.

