## 7.2.6.2 Time to Onset of Biological Response of C-peptide Following MMTT

The biological response of C-peptide is defined as a value >0.2 ng/mL for the C-peptide measurement. For Cohort 2 subjects, time to onset of biological response of C-peptide will be calculated in two ways: the time to onset of biological response from implantation, and the time to biological response within each MMTT.

For the time to onset of biological response from implantation, the time unit will be 'days' and the time itself will be calculated as:

Time to onset of biological response of C-peptide (days) = (Date of first MMTT at which the subject achieved at least one C-peptide > 0.2 ng/mL) – (Date of surgical implantation procedure for the subject) + 1

For the time to onset of biological response within each MMTT, the time unit will be 'minutes' and the time itself will be calculated as:

Time to onset of biological response of C-peptide (minutes) = (Time during MMTT at which the subject first achieved a C-peptide > 0.2 ng/mL) – (Start time of Boost Hi-Protein drink for the MMTT for the subject)

For these time-to-event analyses, subjects who did not achieve biological response will be censored. That is, for the time to onset of biological response of C peptide from implantation, subjects who did not achieve at least one C-peptide > 0.2 ng/mL during any MMTT will be censored at the time they leave the study (complete the study, or withdrawal from the study).

For the time to onset of biological response within each MMTT, subjects who did not achieve at least one C-peptide within a 4-hour MMTT will be censored at 240 minutes. Subjects who did not achieve biological response of C-peptide during a 2-hour MMTT will be censored at 120 minutes.

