## 7.3.7.3 Cohort 2 Secondary Efficacy Analyses

Each of the secondary efficacy endpoints will be analyzed using an  $\alpha = 0.05$  level of significance. Given the large number of secondary efficacy endpoints, the p-values for these endpoints will be considered descriptive.

The FAS will be used to analyze the secondary efficacy endpoints, with the analysis for each endpoint performed within Cohort 2 subjects only. Change from baseline to Weeks 16, 20, 26 and 39 in C-peptide AUC0-2h following an MMTT and change from baseline to Week 52 in C-peptide AUC0-4h following an MMTT; change from baseline to Weeks 16, 20, 26, 39 and 52 in average daily insulin dose in the seven days preceding the clinic visit; and change from baseline to Weeks 16, 20, 26, 39 and 52 in time in euglycemic range, time in hypoglycemic range, and time in hyperglycemic range will each be analyzed using ANCOVA, with treatment group as a factor and the relevant baseline as a covariate.

Time to onset of biological response of C-peptide following an MMTT will be assessed using Kaplan-Meier curves, with the p-value from the logrank test also provided.

The percent of subjects who achieve a positive stimulated C-peptide (defined as > 0.2 ng/mL) after implant; the percent of subjects who achieve a 50% reduction in average weekly exogenous insulin dose from baseline to Weeks 16, 20, 26, 39 and 52; and the percent of subjects who achieve exogenous insulin independence, percent of subjects (of those achieving insulin independence) achieving  $HbA1c \le 7.0\%$  will each be analyzed using Fisher's exact test. The number and percent of subjects in each treatment group and the p-value from the Fisher's test will be provided (at each timepoint, where appropriate).

The percent of time spent with blood glucose values at various cut points as measured by each subject's CGM will be summarized descriptively. The percentages and change from baseline percentages will be summarized for each cut point (<54 mg/dL,  $\ge54$  to <70 mg/dL,  $\ge70$  mg/dL to  $\le180$  mg/dL, >180 mg/dL and >250 mg/dL) and for each treatment group.

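### Time to C-peptide response from implantation censors non-responders after full explant, so the Kaplan-Meier curve can exceed the response rate achieved, and overstates it if failing grafts are removed before later responses.

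*SAP*

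**What the plan says.** SAP 7.2.6.2 sets the event: "The biological response of C-peptide is defined as a value >0.2 ng/mL for the C-peptide measurement". Time from implantation runs to the date of the first MMTT with at least one such value. Subjects who never reach it "will be censored at the time they leave the study (complete the study, or withdrawal from the study", whatever the reason for leaving. Under SAP 7.3.7.3 the endpoint "will be assessed using Kaplan-Meier curves, with the p-value from the logrank test also provided".

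Leaving early goes with loss of the graft:

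- Protocol 13.6.1: "Subjects who are withdrawn prematurely from the study will have the remaining VC-01 units explanted".
- SAP 3.2 allows Cohort 2 treatment to end with the "last unit explanted at Month 12/Week 52 or earlier if requested by the Sponsor". Protocol 13.6 counts a Sponsor-expedited final explant for non-safety reasons as study completion, so that subject is censored early as well.
- Exclusion criterion 30 (Protocol 4.1.2) bars stimulated C-peptide above 0.2 ng/mL at screening, so a later response depends on the implanted units.

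Neither document names a competing event, keeps explanted non-responders at risk, or plans a sensitivity analysis for this endpoint.

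**The concern.** Kaplan-Meier censoring assumes that a censored subject would have gone on to respond at the same rate as those still followed. After full explant that rate is zero. Explant of the last unit before response is therefore a competing event.

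The protocol foresees removals linked to graft function. Section 8.6 lists unexplained graft malfunction requiring explant. Section 13.6 makes damaged or malfunctioning units that cause severe or serious AEs a ground for withdrawal. Section 13.6.1 asks sites to record withdrawal for insufficient response separately. If such subjects leave before others in their group respond, the curve credits them with responses that cannot happen. Treatment group is the number of VC-01-DF units first implanted, so a group with more early removals could look better than one with fewer. The curve would also differ from the crude percentage above the same threshold, with nothing in the SAP to explain why.

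**Working it through.** The plan gives no response rate, explant rate or event count for this endpoint, so there is no figure to reproduce. From the documents come the Cohort 2 size (up to 40) and the MMTT weeks (8, 12, 16, 20, 26, 39, 52). All response and explant counts below are assumptions.

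**Formula.** Let n subjects have *a* responses up to and including the explant week, then *c* non-responders fully explanted and censored, then *b* later responses, with no other early censoring. The product-limit terms telescope to

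1 − KM = 1 − [(n − a)/n] × [(n − a − c − b)/(n − a − c)].

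The proportion achieved is (a + b)/n, and the Aalen-Johansen cumulative incidence equals it. The two agree when c = 0 (no early explant) or b = 0 (no response after the explants).

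**Worked cases, n = 40.**

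- Smallest gap: 8 responders (two each at Weeks 16, 20, 26, 39), 4 explants at Week 26. Here a = 6, c = 4, b = 2: 1 − (34/40)(28/30) = 20.7% against 20%, or 0.7 points.
- Largest gap: 20 responders (2, 4, 4, 4, 4, 2 at Weeks 12, 16, 20, 26, 39, 52), 12 explants at Week 12. Here a = 2, c = 12, b = 18: 1 − (38/40)(8/26) = 70.8% against 50%, or 20.8 points.

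1 − KM for 4, 8 and 12 explants (the 12 responders are two each at Weeks 12, 16, 20, 26, 39, 52):

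| Achieved | Explants at Week 12 | Explants at Week 26 |
|---|---|---|
| 8/40 = 20% | 22.2%, 25.0%, 28.6% | 20.7%, 21.5%, 22.7% |
| 12/40 = 30% | 32.9%, 36.7%, 41.5% | 31.4%, 33.3%, 36.0% |
| 20/40 = 50% | 55.3%, 62.0%, 70.8% | 52.7%, 56.7%, 62.9% |

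If 8 of 40 respond by Week 26 and 12 explants follow at Week 39, both estimates are 20.0%.

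**Small group.** With n = 10 and 4 responders after Week 12 (40% achieved), 2 explants at Week 12 give 1 − 4/8 = 50.0%; 4 explants give 1 − 2/6 = 66.7%.

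**Simulation.** 3,000 trials of 40, with response weeks drawn from the MMTT schedule (probabilities 0.05, 0.10, 0.20, 0.20, 0.25, 0.15, 0.05) and explants at Week 12, 20 or 26. Explanted share is of non-functioning grafts in the related case and of all subjects in the unrelated case.

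| True rate | Share explanted | Related to function: mean 1 − KM (achieved) | Unrelated: mean 1 − KM (achieved) |
|---|---|---|---|
| 20% | 20% | 22.1% (20.1%) | 20.1% (18.1%) |
| 20% | 40% | 24.9% (20.2%) | 20.0% (16.0%) |
| 40% | 20% | 43.2% (40.0%) | 40.1% (36.1%) |
| 40% | 40% | 47.2% (39.8%) | 39.9% (32.0%) |

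Related removal lifts the mean by about 2 to 7 points. Unrelated removal leaves 1 − KM at the true rate while the achieved rate falls below it.

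**Logrank.** Take two groups of 20, each with 8 responses at Day 183, and 10 non-responders explanted at Day 100 in one group only. At Day 183 the numbers at risk are 10 and 20, with 16 events. Expected events in the explant group are 16 × 10/30 = 5.33; the variance is 16 × (10/30)(20/30)(14/29) = 1.717; z = (8 − 5.33)/√1.717 = 2.04, p = 0.04. The curves read 80% and 40%, although 40% responded in each group. With 8 explants p = 0.15; with 4, p = 0.55.

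**The case against.** The bias is conditional. A reader might infer that Kaplan-Meier always overstates response here; it does not when removal is unrelated to function or follows the last response.

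A reader might also infer that failing grafts will be removed on C-peptide results, because Protocol 3.2 says "The Sponsor will review available C-peptide results from ongoing subjects". The same sentence gives the purpose as choosing the number of units for later subjects. It shows access to the data, not an explant rule. The note on Sponsor-expedited explant in Protocol 13.6 has collecting explant data by Week 12 as its only example. Insufficient response appears in 13.6.1 as a recording instruction and is not among the withdrawal criteria in 13.6. Removal linked to function is foreseen, mainly through malfunction, but no rule plans it for low C-peptide.

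Cumulative incidence has a cost too. It counts a Sponsor-expedited explant as non-response, although Protocol 5.1 expects maturation over three to six months. It describes what was achieved under the explant policy, while Kaplan-Meier under unrelated removal describes the product left in place. The SAP does not say which it wants. The logrank test with explants censored compares cause-specific hazards, a legitimate quantity that does not compare proportions responding; the p = 0.04 example needs half a group explanted.

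The plan has safeguards. The crude percentage above 0.2 ng/mL is reported by group with Fisher's exact test, premature VC-01-DF explants are summarised with reasons (SAP 7.3.3), and premature explants are listed (SAP 7.3.7.2).

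All of this stands and limits the point. It does not supply a target for the curve or make a fully explanted subject able to respond.

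**Conclusion.** The point holds in conditional form. The censoring rule treats full explant as ordinary loss to follow-up, so the curve need not match the response achieved. Overstatement of the proportion responding requires removal related to graft function and at least one later response in the group. The ranges of about 0.7 to 21 points (fixed counts) and 2 to 7 points (simulated means) rest wholly on assumed rates.

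The reach is narrow. A reader might fear for the trial's efficacy conclusion, but the primary endpoint, the crude responder percentage and the within-MMTT analysis (censored at 120 or 240 minutes) are unaffected. Subjects who lose up to two VC-01-DF units may stay in the study and at risk. The SAP tests no hypotheses and calls the secondary p-values descriptive. This is a cheap improvement to one secondary analysis.

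**What to change.** In SAP 7.2.6.2 and 7.3.7.3, for time to response from implantation:

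1. State that the target is the proportion responding under the actual explant policy.
2. Treat explant of the last VC-01 unit before response as a competing event, and report the Aalen-Johansen cumulative incidence per treatment group.
3. Keep the current Kaplan-Meier and logrank analysis as a sensitivity analysis, and show early explants by reason beside the curve.

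If explanted subjects are instead kept in the risk set as non-responders, hold them beyond the last possible Week 52 MMTT. Day 365 is too early: the ±7-day window around target Day 365 allows an MMTT on Day 372. Assume 10 subjects, 4 of them explanted and held to Day 365, 2 responses on Day 183, 2 on Day 370, and 2 others followed without response. Then 1 − KM = 1 − (8/10)(2/4) = 60% against 40% achieved.

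The cost is a few lines of SAP text and a standard procedure. Explant dates are already needed for exposure (SAP 7.3.3), and the early termination visit includes a 4-hour MMTT, so response status at removal should usually be known. The downside is a lower reported curve wherever early explants occur, including Sponsor-expedited ones.

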# 7.2.6.3 Average Daily and Weekly Exogenous Daily Insulin Dose and Exogenous Insulin Independence

Exogenous daily insulin dose logs will be completed via subject diary by subjects in Cohort 2. Investigators will review the exogenous insulin dose logs completed by the subjects at each study visit. Determination of exogenous insulin dosage levels and exogenous insulin independence for Cohort 2 subjects will be determined based on the subjects' insulin dose logs.

Blank values in the insulin log are not considered to be 0 values.

## 7.2.6.3.1 Daily and Weekly Exogenous Insulin Dose

For subjects in Cohort 2, baseline average daily and average weekly exogenous insulin dose requirements will be calculated using up to 28 days of data. Baseline average daily and average weekly insulin requirements will be calculated using data starting at Day -1 (the day prior to implant) and working backwards for up to 28 days (through Day -28). For instances in which the available pre-implant data provides less than 28 days of data, post-implant data will be used to supplement, using Day 4 forward until 28 days of data are available. Data from days on which an MMTT or SOGCT was performed, will not be included in the calculation.

At Weeks 16, 20, 26, 39 and 52, the last 7 daily total exogenous insulin doses recorded in the log will be used to calculate the average daily and weekly exogenous insulin dose at that visit. The last 7 daily records must be within the previous 14 calendar days and may not include a day in which an MMTT or SOGCT was performed. There must be at least 4 different days worth of data for a particular timepoint to be considered evaluable.

The weekly average value will be calculated as:

7 \* (sum of the insulin doses during the period / number of days with insulin doses in the period).

The percent reduction in average weekly exogenous insulin dose from baseline at these visits will be calculated as:

(Average weekly insulin dose at post-baseline visit - baseline average weekly insulin dose)\*100/ baseline average weekly insulin dose.

